6.5.11. Management of Potential Study Intervention-Related Toxicities

6.5.11.1. Cytokine Release Syndrome

Symptoms associated with CRS vary greatly and may be difficult to distinguish from other conditions. The more common symptoms include fever, nausea, headache, tachycardia, hypotension, rash and shortness of breath. The severity of symptoms can be mild to life threatening and thus there should be a high suspicion for CRS if these symptoms occur. If CRS is suspected, cytokines will be analyzed at central laboratories to determine if cytokine elevation consistent with CRS is observed (see [Section 8.2.5](#)). The severity of CRS will be assessed according to the modified grading described by ASTCT ([Lee et al, 2019](#)) and captured on the AE CRF and on the CRS CRF as described in [Appendix 9](#).

CRS should be managed according to the CRS Mitigation and Management guidance in [Appendix 9](#) or per local institutional guidelines.

6.5.11.2. Injection Site Reactions:

ISR may be immediate, although it usually appears within 24-48 hours after injection. ISR, by definition, includes the following: erythema, pruritus, pain, inflammation, rash, induration, itching and edema at the injection site. To evaluate ISRs, site tolerability assessments will be performed per [SoA](#).

Topical corticosteroids and topical or systemic antihistamines may be applied to treat any rash or pruritis at the injection site.

6.5.11.3. Hypersensitivity Reactions Types 1 and 3:

Type 1 hypersensitivity or allergic (eg, shortness of breath, urticaria, anaphylaxis, angioedema) reactions are theoretically possible in response to any injected protein. Immune complex mediated Type 3 hypersensitivity reactions are similar to the AEs of Type 1 reactions but are likely to be delayed from the time of injection and may include symptoms such as rash, urticaria, polyarthritis, myalgia, polysynovitis, fever, and, if severe, glomerulonephritis.

All participants should be closely observed while receiving PF-07209960 injection and monitoring will continue thereafter for clinical signs of allergic reactions/hypersensitivity.

In the case of a hypersensitivity reaction, the participant will be treated symptomatically with supportive care, further monitoring, and treatment with anti-histamines and/or corticosteroids. Study intervention may be stopped, and the participant will be followed until the end of the study.

6.5.11.4. Infusion Related Reactions

IRRs are reactions that occur during or following an infusion of the study intervention. IRRs may present with different symptoms and are most commonly characterized by fever and chills, and less commonly hypotension or dyspnea. IRRs can typically be distinguished from CRS by their timing. IRRs usually occur during administration of the study intervention while CRS is delayed until several hours or days after administration of the study intervention. In the event of infusion related reactions, investigators should institute treatment measures according to best medical and nursing practice.

Premedication is not required but may be implemented at the investigator's discretion. If a participant experiences an IRR, premedication is recommended prior to subsequent infusions (eg, diphenhydramine and acetaminophen) approximately 0.5 to 2 hours before PF-07209960 administration. This regimen may be modified based on local standards; however, corticosteroids are not recommended. The pretreatment medications will not be supplied by Pfizer.

Detailed guidance on treatment, dose interruptions and potential retreatment of IRRs is provided in [Appendix 15](#).

6.5.11.5. Immune-Related Adverse Events

irAEs are toxicities resulting from the non-specific activation of the immune system that can affect almost any organ system. Several irAEs have been described in association with the use of ICIs therapies including anti-PD-1, anti-PD-L1 and anti-CTLA-4. The most common irAEs described with ICIs are those involving the cutaneous, endocrine, gastrointestinal, pulmonary, hepatic and musculoskeletal systems. In addition, less frequent irAEs include those involving the cardiovascular, renal, pancreatic, neurological, ophthalmological, and hematological systems. In rare cases, irAEs may be life-threatening or lead to death.

Treatment of irAEs is mainly dependent on severity. In general, Grade 1 or 2 irAEs are treated symptomatically with persistent Grade 2, Grade 3 or Grade 4 irAEs managed with moderate to high dose corticosteroids and/or hormonal therapy for immune-related

Guidelines for the treatment of irAEs are provided in [Appendix 14](#).

6.6. Dose Modification

Every effort should be made to administer study intervention on the planned dose and schedule. In the event of significant toxicity, dosing may be delayed and/or reduced as described below. In the event of multiple toxicities, dose modification should be based on the worst toxicity observed. Participants are to be instructed to notify investigators at the first occurrence of any adverse symptom.

In addition to dose modifications, investigators are encouraged to employ best supportive care according to local institutional clinical practices.

Toxicities potentially related to PF-07209960 should be managed according to the dose modifications described in [Table 4](#).

Selected toxicities that do not resolve or worsen following supportive care and dose modifications and with a clinical presentation consistent with a potential irAE without a clear alternative explanation, may require treatment with corticosteroids or other immunosuppressants and should be managed according to the management of irAEs as described in [Appendix 14](#).

CRS should be managed according to the CRS Mitigation and Management guidance as described in [Appendix 9](#).

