6.6.3. Dose Reductions

Following dosing interruption or cycle delay due to toxicity, the PF-07209960 dose may need to be reduced when treatment is resumed.

No specific dose adjustments are recommended for Grade 1/2 treatment-related toxicity. However, participants experiencing recurrent and intolerable Grade 2 toxicity may resume dosing at the next lower dose level based on investigator's medical judgment once recovery to Grade ≤ 1 or baseline is achieved.

Dose reduction of PF-07209960 by 1 dose level (with maximum reduction to dose level -1, 0.3 mg SC, 0.06 mg IV) ([Table 2](#)) will be allowed depending on the type and severity of toxicity encountered. Participants requiring more than 1 dose reduction will be discontinued from the treatment and entered into the follow-up phase, unless otherwise agreed between the investigator and the sponsor. All dose modifications/adjustments must be clearly documented in the participant's source notes and CRF.

Once a dose has been reduced for a given participant, all subsequent cycles should be administered at that reduced dose level, unless further dose reduction is required. Intraparticipant dose re-escalation may be allowed after discussion between the investigator and sponsor. Participant must not experience a Grade 2 or higher adverse event to be eligible for intraparticipant dose re-escalation.

Table 3. Available Dose Reduction Levels From Starting Dose

Dose Level ^a	SC	IV ^b
Starting	CC1	

a. PF-07209960 dose de-escalation below -1 dose level is not allowed.

b. IV infusion over 1 hour (± 10 minutes)

Participants experiencing a DLT may resume dosing at the next lower dose level (if applicable) once adequate recovery is achieved, and in the opinion of the investigator and sponsor, the participant is benefiting from therapy.

For management of immune-related adverse events, please refer to [Appendix 14](#). For all other toxicities, recommended dose reductions for study intervention are described in Table 4.

Table 4. Treatment Dose Modifications for Study Intervention-Related Toxicity

Toxicity	Grade 1	Grade 2	Grade 3	Grade 4

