Nonhematologic	Continue at the same dose level.	Continue at the same dose level.	Withhold dose until toxicity is Grade ≤ 1 , or has returned to baseline, then resume treatment at the same dose level or reduce the dose by 1 level at the discretion of the investigator*.	Withhold dose until toxicity is Grade ≤ 1 , or has returned to baseline, then reduce the dose by 1 level and resume treatment, or discontinue at the discretion of the investigator*.
Hematologic (except lymphopenia)	Continue at the same dose level.	Continue at the same dose level.	Withhold dose until toxicity is Grade ≤ 2 , or has returned to baseline, then resume treatment at the same dose level**.	Withhold dose until toxicity is Grade ≤ 2 , or has returned to baseline, then reduce the dose by 1 level and resume treatment**.

* Nausea, vomiting, or diarrhea must persist at Grade 3 or 4 despite maximal medical therapy to require dose modification.

** Cycle will not be extended to cover for the missing doses.

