Grade 3 to 4 Grade 3: Covering >30% body surface area; Grade 4: Life threatening consequences	Withhold study treatment for Grade 3 Permanently discontinue for Grade 4 or reswne to Grade 3 Consider skin biopsy Dermatology consult 1.0 to 2.0 mg/kg/day prednisone or equivalent Add prophylactic antibiotics for opportunistic infections	If improves to Grade I: Taper steroids over at least 1 month; reswne study treatment following steroids taper (for initial Grade 3).

Pulmonary irAEs		
Grade of Pneumonitis (NCI-CTCAE v5.0)	Initial Management	Follow-up Management
Grade 1 !Radiographic changes only	Consider withholding study treatment Monitor for symptoms every 2 to 3 days Consider Pulmonary and Infectious Disease consults	Re-assess at least every 3 weeks. If worsens: Treat as Grade 2 or Grade 3 to 4.
Grade 2 Mild to moderate new symptoms	Withhold study treatment Pulmonary and Infectious Disease consults Monitor symptoms daily; consider hospitalization 1.0 to 2.0 mg/kg/day prednisone or equivalent Add prophylactic antibiotics for opportunistic infections Consider bronchoscopy, lung biopsy	Re-assess every 1 to 3 days If improves: When symptoms return to Grade ::1, taper steroids over at least 1 month, and then resume study treatment following steroids taper. If not improving after 2 weeks or worsening: Treat as Grade 3 to 4.
Grade 3 to 4 Kirade 3: Severe new symptoms; New/worsening hypoxia; Kirade 4: Life-threatening	Permanently discontinue study treatment. Hospitalize Pulmonary and Infectious Disease consults 1.0 to 2.0 mg/kg/day prednisone or equivalent Add prophylactic antibiotics for opportunistic infections Consider bronchoscopy, lung biopsy	If improves to Grade ::1: Taper steroids over at least 1 month. If not improving after 48 hours or worsening: Add additional immunosuppression (for example, infliximab, cyclophosphamide, IV immunoglobulin, or mycophenolate mofetil).

Hepatic irAEs		
Grade of Liver Test Elevation (NCI-CTCAE v5.0)	Initial Management	Follow-up Management
Grade 1 KJgrade I AST or ALT >ULN to . .0x ULN and/or Total bilimbin ULN to 1.5 x ULN	Continue study treatment	Continue liver function monitoring If worsens: Treat as Grade 2 or 3 - 4.
Grade 2 ST or ALT >3.0 to 5 x ULN and/or total bilimbin >1.5 to 3 x IULN	Withhold study treatment Increase frequency of monitoring o evely 3 days	If returns to Grade 1 : Resume routine monitoring; resume study treatment. If elevation persists >5 to 7 days or worsens: Treat as Grade 3 to 4.

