Grade 3 to 4 ST or ALT >5 x ULN and/or total bilimbin >3 x ULN	Pennantly discontinue study reatment Increase frequency of monitoring o evely 1 to 2 days 1.0 to 2.0 mg/kg/day prednisone or equivalent Add prophylactic antibiotics for opportunistic infections Consult gastroenterologist/ hepatologist Consider obtaining MRI/CT scan of liver and liver biopsy if clinically wa1rnted	If returns to Grade 1 : Taper steroids K>ver at least 1 month. If does not improve in >3 to 5 days, worsens or rebounds: Add niycophenolate mofetil 1 gram (g) tv.ice klaily. If no response within an additional 3 to 15 days, consider other immunosuppressants per local iguidelines.

Renal irAEs		
Grade of Creatinine Increased (NCI-CTCAE v8.0)	Initial Management	Follow-up Management
K;rade 1 K=:reatinine increased >ULN to 1.5 x IULN	Continue study treatment	Continue renal function monitoring. If worsens: Treat as Grade 2 o 3 or 4.
K;rade 2 to3 t:reatinine increased >1.5 and ::;6 x IULN	Withhold study treatment Increase frequency of monitoring to every 3 days 1.0 to 2.0 mg/kg/day prednisone or equivalent. Add prophylactic antibiotics for opportunistic infections Consider renal biopsy	If returns to Grade ::;1: Taper steroids over at least 1 month, and resume study treatment following steroids taper. If worsens: Treat as Grade 4.
K;rade 4 K=:reatinine increased >6 x ULN	Permanently discontinue study treatment Monitor creatinine daily 1.0 to 2.0 mg/kg/day prednisone or equivalent. Add prophylactic antibiotics for opportunistic infections Consider renal biopsy Nephrology consult	If returns to Grade ::;1: Taper steroids over at least 1 month.

Cardiac irAEs		
Myocarditis	Initial Management	Follow-up Management

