New onset of cardiac signs or symptoms and / or new laboratory CCI [REDACTED] or cardiac imaging abnormalities suggestive of myocarditis	
Withhold study treatment
 
Hospitalize
 
In the presence of life threatening cardiac decompensation, consider transfer to a facility experienced in advanced heart failure and arrhythmia management
 
Consult cardiologist to establish etiology and rule-out immune-mediated myocarditis
 
Guideline based supportive treatment as per cardiology consult*
 
Consider myocardial biopsy if recommended per cardiology consult
	
If symptoms improve and immune-mediated etiology is ruled out, re-start study treatment.
 
If symptoms do not improve/worsen, viral myocarditis is excluded, and immune-mediated etiology is suspected or confirmed following cardiology consult, manage as immune-mediated myocarditis.

none-mediated myocarditis	
Permanently discontinue study treatment
 
Guideline based supportive treatment as appropriate as per cardiology consult.* 1.0 to 2.0 mg/kg/day prednisone or equivalent
 
Add prophylactic antibiotics for opportunistic infections
	
Once improving, taper steroids over at least 1 month.
 
If no improvement or worsening, consider additional immunosuppressants (eg, azathioprine, cyclosporine A).

*Local guidelines, or eg, ESC or AHA guidelines

ESC guidelines website: <https://www.escardio.org/Guidelines/Clinical-Practice-Guidelines>

AHA guidelines website:

<http://professional.heart.org/professional/GuidelinesStatements/searchresults.jsp?q=&y=&t=1001>

Endocrine irAEs		
Endocrine Disorder	Initial Management	Follow-up Management
Grade 1 or Grade 2 endocrinopathies (hypothyroidism, hyperthyroidism, adrenal insufficiency, type I diabetes mellitus)	
 -Continue study treatment -Endocrinology consult if needed -Start thyroid hormone replacement therapy (for hypothyroidism), anti-thyroid treatment (for hyperthyroidism), corticosteroids (for adrenal insufficiency) or insulin (for Type I diabetes mellitus) as appropriate -Rule-out secondary endocrinopathies (ie, hypopituitarism / hypophysitis) 	
 -Continue hormone replacement/suppression and monitoring of endocrine function as appropriate.

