Grade 2 or Grade 3 clinical signs or symptoms suggestive of a potential irAE	
 -Withhold study treatment pending clinical investigation 	
 -If irAE is ruled out, manage as appropriate according to the diagnosis and consider restarting study treatment -If irAE is confirmed, treat as Grade 2 or 3 irAE.
Grade 2 irAE or first occurrence of Grade 3 irAE	
 -Withhold study treatment -1.0 to 2.0 mg/kg/day prednisone or equivalent -Add prophylactic antibiotics for opportunistic infections -Specialty consult as appropriate 	
 -If improves to Grade ::SI: -Taper steroids over at least 1 month and resume study treatment following steroids taper.
Recurrence of same Grade 3 irAEs	
 -Permanently discontinue study treatment -1.0 to 2.0 mg/kg/day prednisone or equivalent -Add prophylactic antibiotics for opportunistic infections -Specialty consult as appropriate 	
 -If improves to Grade ::;1 : -Taper steroids over at least 1 month.
Grade 4	
 -Permanently discontinue study treatment -1.0 to 2.0 mg/kg/day prednisone or equivalent and/or other immunosuppressant as needed -Add prophylactic antibiotics for opportunistic infections -Specialty consult 	
 -If improves to Grade ::;1 : -Taper steroids over at least 1 month.
Requirement for 10 mg per day or greater prednisone or equivalent for more than 12 weeks for reasons other than hormonal replacement for adrenal insufficiency	
 -Permanently discontinue study treatment -Specialty consult 	
Persistent Grade 2 or 3 irAE lasting 12 weeks or longer		

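### Section 6.6 sends a suspected Grade 2 immune-related event to Table 4, which continues dosing, while 6.6.3 and Appendix 14 would withhold; the gap falls mainly on a dosing day before supportive care is judged to have failed

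*Protocol*

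**What the plan says.** Three parts of the protocol decide what happens to a suspected immune-related adverse event (irAE).

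- **Section 6.6, opening text.** Any toxicity potentially related to the study drug goes to Table 4. A second group is then described: "Selected toxicities that do not resolve or worsen following supportive care and dose modifications and with a clinical presentation consistent with a potential irAE", with no clear alternative explanation. These may need corticosteroids or other immunosuppressants and are to be managed under Appendix 14. This is the only route to Appendix 14 that the opening text names, and it sets no time limit for judging that an event has not resolved.
- **Section 6.6.3 and Table 4.** irAEs are referred to Appendix 14 directly, with no failure step, and then: "For all other toxicities, recommended dose reductions for study intervention are described in Table 4". The nonhematologic Grade 2 entry in Table 4 is "Continue at the same dose level".
- **Appendix 14 (10.14).** For Grade 2 pneumonitis: "Withhold study treatment Pulmonary and Infectious Disease consults Monitor symptoms daily; consider hospitalization". Grade 2 liver tests are also a hold, with "Resume routine monitoring; resume study treatment" once they are back to Grade 1. Renal Grade 2 to 3 is a hold with prednisone, and on recovery: "Taper steroids over at least 1 month, and resume study treatment following steroids taper". The cardiac row starts from new signs, laboratory findings "or cardiac imaging abnormalities suggestive of myocarditis", with no grade stated. The row for 'other' irAEs acts on Grade 2 or 3 signs that are only suggestive: "Withhold study treatment pending clinical investigation".

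**The concern.** A rule that acts on suspicion cannot work if the site reaches it only after supportive care has failed. The condition in 6.6 also assumes that dose modifications have been tried, but Table 4 prescribes none at Grade 2, so the point of hand-over is undefined.

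Two things are at stake. The first is safety: in a first-in-human study, a site following 6.6 as written can give a dose that another stated rule says to hold. Abnormal liver function, abnormal renal function and irAEs including myocarditis are all listed as events of special interest (8.3.8). The second is Part 1 data: the route chosen can decide whether a participant counts in the dose-toxicity model.

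**Working it through.** The plan gives no figure here to reproduce. The check sets the rules side by side and then works through the Cycle 1 calendar.

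**1. Dosing instruction by route**

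| Suspected event | 6.6 to Table 4 | 6.6.3 to Appendix 14 | Conflict |
|---|---|---|---|
| Pneumonitis, Grade 2 | continue | withhold, steroids | yes |
| Liver tests, Grade 2 | continue | withhold until Grade 1 | yes |
| Creatinine, Grade 2 | continue | withhold, steroids | yes |
| 'Other' irAE, Grade 2 | continue | withhold while investigating | yes |
| Myocarditis signs, Grade 1-2 | continue | withhold, hospitalize | yes |
| Rash, Grade 1-2, first presentation | continue | continue | no |
| Endocrinopathy, Grade 1-2, other than hypophysitis | continue | continue | no |
| Diarrhea/colitis, Grade 2 | continue | withhold | settled by 6.5.6, which sends suspected cases to Appendix 14; the Table 4 footnote lacks that limit |

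**2. When the conflict matters.** Dosing is every 2 weeks (6.1.1). An event that supportive care has failed to resolve reaches Appendix 14 on either route. A liver event back to Grade 1 by the dosing day is dosed on either route. What remains is mainly an event present on a dosing day before failure has been judged. For lung, kidney and confirmed 'other' events the taper also keeps the hold in force after recovery.

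**3. Part 1 calendar**

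Inputs:
- Doses fall on Days 1 and 15 of a 28-day cycle.
- Without a DLT, evaluability needs 2 doses in Cycle 1 (4.3.3).
- Under the pulmonary, renal and confirmed-other rows, dosing resumes only after a taper of at least 1 month. One month is taken as 28 days, the shortest reading.
- Cohorts are about 2-4 participants (9.2.1).

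Earliest restart = s + 28, where s is the day the taper starts.
- s = 8: 8 + 28 = Day 36.
- s = 15: 15 + 28 = Day 43.
- Any s of 1 or more gives Day 29 or later, which is after Day 28. A hold covering Day 15 therefore never leaves room for a second Cycle 1 dose.

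Time since the Day 1 dose = restart day - 1.
- 36 - 1 = 35 days and 43 - 1 = 42 days, both over 28.
- Only s = 1 gives exactly 28 days, and that would need onset and recovery on the dosing day itself.
- Beyond 4 weeks from the last dose, 6.6.2 makes permanent discontinuation the default, unless the investigator's benefit/risk assessment supports otherwise after discussion with the medical monitor.

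The participant then has one Cycle 1 dose and is non-evaluable and replaceable, unless a DLT applies under 4.3.3. Candidates are Grade 2 pneumonitis not resolved to Grade 1 or lower within 72 hours of starting maximal supportive care, a delay of 4 weeks or more to the next cycle, or a significant dose delay judged a DLT on review. One participant is 1/4 = 25% to 1/2 = 50% of a cohort.

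Under Table 4 the same participant, if the event resolves with supportive care, receives both doses and counts as a non-DLT.

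For myocarditis the issue is safety only: confirmed immune-mediated myocarditis of any grade is already a DLT.

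**The case against.** The best defense is that the protocol read as a whole gets there. Section 6.6 does not forbid earlier use of Appendix 14, and its sentence is largely about events that may need steroids. Section 6.6.3, which introduces Table 4, sets its scope. Section 6.6.1 relies on Appendix 14 for resumption, and Section 8 requires safety issues to be discussed with the sponsor immediately. This stands in part: a careful site may well withhold, and silent divergence between sites is less likely. But none of these places says when a suspected event counts as an irAE. The 6.6 sentence hands over management, not just steroids. The freedom in 6.6 to delay for significant toxicity is tied to the rules that follow it, and at Grade 2 those say continue. Section 6.5.6 shows that suspicion-based routing was written down for one organ only.

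Four stronger readings are tempting but not supported.

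- A reader might infer that every suspected Grade 2 irAE is dosed through. The 2-week interval and the failure condition in 6.6 confine this mainly to the dosing-day window, for lung and kidney largely as for liver.
- A reader might count two missed doses against none, with Cycle 2 starting 7 or 14 days late (36 - 29 and 43 - 29). That assumes a restart, which 6.6.2 allows only as an exception.
- A reader might see 6.5.11.5 as a further contradiction. It is a general statement that defers to Appendix 14, and its sentence is cut off in the available text.
- A reader might conclude that Appendix 14 should govern at every grade from first suspicion. It permanently discontinues for AST or ALT above 5 x ULN and for Grade 3 pneumonitis, where Table 4 holds and may resume. Transaminase elevation is a reported toxicity of recombinant IL-15 (2.2.4), and participants with liver involvement may enter at up to 5 x ULN (5.1). Mere suspicion should not end treatment.

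**Conclusion.** The concern holds as a contradiction between stated dosing rules, not as missing detail. It should be corrected in the next amendment. It covers suspected Grade 2 lung, liver, kidney and 'other' irAEs and suspected myocarditis, mainly when present on a dosing day before supportive care is judged to have failed. For the liver the window is narrow.

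In Part 1 the size is one participant, 25-50% of a cohort until replaced, who is evaluable on one route and non-evaluable, with discontinuation as the default, on the other. The documents do not say how often this would happen, and no rate is assumed.

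The conclusion rests on three assumptions: a month is at least 28 days; the event on the Table 4 route resolves with supportive care; and evaluability follows Protocol 4.3.3. SAP Table 2 adds a threshold of 75% of planned doses, which one of two doses (50%) also fails. The irAE mitigation text in 2.3.1 is partly redacted, so the conclusion rests on the visible text.

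**What to change.** Replace the routing sentences in 6.6 with text to this effect:

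> When an irAE of Grade 2 or higher, or myocarditis of any grade, is suspected without a clear alternative explanation, withhold study intervention while it is investigated, except where Appendix 14 continues treatment (eg, Grade 1-2 rash or endocrinopathy). Once an irAE is confirmed or remains the most likely cause, Appendix 14 governs, including steroids and permanent discontinuation. Table 4 applies to toxicities not suspected to be immune-related. CRS remains under Appendix 9.

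Keep the condition about failure to resolve or worsening only for escalation to immunosuppressants where Appendix 14 does not already require them. Limit the Table 4 footnote on diarrhea to events not suspected to be immune-related, in line with 6.5.6. Evaluability needs no new text, because 4.3.3 already covers a participant with one Cycle 1 dose and no DLT.

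The cost is a short rewording of 6.6 and one footnote in an amendment. In conduct, expect some additional Grade 2 holds and possibly some replaced or discontinued Part 1 participants, in a number the documents do not allow to be estimated.
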